## 1 Study Summary

Title	PILOT: Evaluation of the new FDA warning labels: Does highlighting lesser known harms of tobacco use increase attention, recall and knowledge of tobacco harms compared to well-known harms?
Short Title	FDA Labels: Eye Tracking Study
IRB Number	843703
Methodology	
This laboratory-based study will aim to enroll 70 current cigarette users to complete a 1-day cross-sectional, randomized, parallel design protocol.
 
The participants will be randomized to one of two conditions, pictorial warning labels (PWLS) with well-known versus lesser-known tobacco harms. After completing a baseline questionnaire, the participants will view about 4 labels from the assigned group and complete a follow-up questionnaire. Eye-tracking equipment will provide data on visual processing of the warning labels and the effect of these labels on knowledge, attitudes and beliefs about smoking will be supplemented by self-report.

Study Center(s)	Single-center
Objectives	
Aim 1: To assess daily smokers' response to FDA PWL content on visual engagement, recall and knowledge
 
Aim 2: To conduct a laboratory-based study to evaluate effects of PWL risk content (lesser-known vs well-known risks) on visual engagement, recall and knowledge

Number of Participants	70 participants (randomized)

Main Inclusion and Exclusion Criteria	
Main Inclusion:
 

1. Current cigarette smokers who smoke at least 5 cigarettes per day who are between 21 and 65 years of age. Participants must physically present a pack of their preferred brand of cigarettes during the session to confirm their status as a regular cigarette smoker.

2. Not currently undergoing smoking cessation treatment or planning to quit smoking.

 
Main Exclusion:
 

1. Use of any nicotine-containing products other than cigarettes. Participants reporting isolated use of other nicotine containing products less than 5 times per month are eligible to participate.

2. Current or impending enrollment in a smoking cessation program. Further, participants will be excluded for an attempt to quit smoking over the duration of the study period.

3. Lifetime history or current diagnosis of COPD, cardiovascular disease, or heart attack.

 
The complete list of study inclusion and exclusion criteria is included within the Characteristics of the Study Population section of this protocol.

--	--

## 2 Introduction

### 2.1 Background

The Food and Drug Administration (FDA), while implementing a provision of the Family Smoking Prevention and Tobacco Control Act (TCA), issued new cigarette health warnings for cigarette packages on August 15, 2019 (84 FR 42754). Pictorial warning labels (PWLs) are an effective way to communicate health risks of tobacco use  and research evidence from many countries shows a significant increase in awareness of smoking harms as a result of PWL exposure . Multiple research studies have emphasized the effectiveness of pictorial warning labels compared to text-only warnings for increasing knowledge regarding smoking risks, likelihood to reduce cigarette demand and promoting quitting . Despite the general assumption that smokers are aware of risks associated with smoking, even in high income countries such as United States and Canada – significant gaps in health knowledge remain . The newly released warning labels include lesser-known harms of smoking such as macular degeneration, bladder cancer and erectile dysfunction. Currently, there is limited evidence on the effect of lesser-known harm warnings on attention, recall and knowledge increase of tobacco related harms.

This study, as a part of Pilot Project of the Tobacco Centers of Regulatory Science (TCORS), will examine the effect of the newly proposed FDA PWLs on daily smokers on visual engagement, knowledge, and recall.

It is as an exploratory experimental study using objective measures and self-report survey. We will recruit 70 daily smokers to participate in a single-session laboratory-based study. The participants will be assigned to either the lesser-known harm group or well-known harm group of PWLs. They will first view 4 warning labels in a randomized order from the assigned group following which they will view all 11 warnings and rank them based on avoidance, preference and being most informative. Primary outcomes will be eye-tracking measures, correct recall of text, image and message, knowledge of tobacco harms and risk-perceptions.

**This document is a human research protocol for a TCORS Pilot Study.** This study will be conducted in compliance with this research protocol and according to U.S. standards of Good Clinical Practice (GCP), applicable government regulations, and institutional research policies and procedures.

## **2.2 *Rationale***

### **2.2.1) Rationale for between subject condition – warning labels**

The new warning labels are created in compliance with court recommendations and tailored to increase knowledge of smoking harms. 6 out of 11 warning labels highlight lesser-known smoking harms. The participants will be randomized to one of two conditions – one containing FDA warning labels bearing lesser known and another with better-known tobacco use risks. In Canada, packages include information about smoking causing impotence and therefore, twice as many respondents reported impotence as tobacco harm relative to respondents in US, UK and Australia. There have been no previous studies that have evaluated the impact of highlighting lesser known harms of tobacco; they are now a part of FDA's label policy and would add to the literature on tobacco control messaging.

### **2.2.2) Rationale for primary outcome measures**

Previous PWL studies using eye-tracking methodology have used latency, latency duration and total dwell time to characterize visual engagement and this study will continue to use these measures for consistency and comparisons. The image/text/message recall and knowledge measures are a good indicator of information retention and effectiveness of the labels.

## **3 Study Objectives**

**Aim 1:** To assess daily smokers' response to FDA PWL content on visual engagement, recall and knowledge.

H1a: Warning label images may have greater visual engagement when compared to text portions of the PWLs

H2a: The recall for image areas of PWLs might be higher post-exposure in comparison to text areas of interest.

**Aim 2: To evaluate effects of PWL risk content (lesser-known vs well-known risks) on visual engagement, recall and knowledge**

H2a: Warning labels bearing images of lesser known tobacco use harms will have longer latency and fixation durations than warning labels bearing images of well-known harms of tobacco.

H2b: The initial image/text/gist recall of PWL text and message with lesser known harms may be lower than well-known harms.

H2c: The knowledge increase will be greater among smokers exposed to warning labels highlighting lesser known harms of tobacco.

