## **4 Study Design**

### ***4.1 Design***

Study participants will be randomized to view one set of graphic warning labels with either lesser-known or well-known harms of tobacco use. The labels will be presented on a computer screen while their eye movements are recorded for each label seen. Participants will provide smoking and quitting related attitude, belief and intention measures and answer questionnaires before and after viewing the labels during the in-person session. This laboratory-based study will aim to enroll 70 current cigarette users to complete a 1-day, randomized, parallel design protocol. We base this design on our previous and ongoing studies using eye-tracking methodology.

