### ***4.2 Study Duration***

Recruitment/enrollment is anticipated to begin in November 2020. We estimate that up to 70 participants will be randomized and complete the study within a year. Each participant will attend the single, 2-hour study session.

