### ***5.2 Accrual***

We have ongoing projects with current smokers who meet the criteria for the study. At the conclusion of those studies, we ask participants if we can contact them regarding future research opportunities. Further, we will post flyers and advertise online, similar to our previous recruiting efforts. We will enroll (i.e., sign an IRB-approved informed consent form) ~70 participants to . To achieve this goal, we intend to recruit 5-7 participants per month, which will allow us to enroll and randomize enough participants to complete data collection as proposed. The sample size was determined based on a previous graphic warning label eye-tracking study by Mercincavage et al.

and Lochbuehler et al. which was sufficiently powered to detect effects of a content attribute (congruency) on eye-tracking measures and image/text/message recall. In order to maximize participation in the study we will: (1) educate participants about the benefits of participation and the knowledge gained from the study; (2) schedule sessions at times convenient for participants; (3) provide reminder calls, emails, and potentially texts; and (4) provide payment for completion of the study visit and study requirements.

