### 5.8 *Procedures*

The lab session will occur at the Center for Interdisciplinary Research on Nicotine Addiction (CIRNA). Participants will typically receive a session reminder 24 – 48 hours prior to their scheduled session via phone call, email, and text message (if applicable).

During the session (Duration: ~2 hours), participants will complete the following:

1. Confirm the accuracy of information (i.e., name, address, phone number, email [if applicable], date of birth, age, ethnicity, race, sex assigned at birth, gender, cigarette brand type) provided during the initial Telephone Eligibility Screen. Participants will be explicitly instructed to bring in their own preferred brand of cigarettes to verify their preferred brand. If the participant does not bring in the brand of cigarettes, they reported during the Telephone Eligibility Screen, the participant may be deemed ineligible or their session may be rescheduled to a later time/day.
2. Receive and review a research study summary for potential participants. If the participant is still interested in participating in the study, they will be presented with the complete combined Informed Consent Form per below.
3. Be presented with the combined Informed Consent Form. The Informed Consent Form will be read to the participant verbatim. All of the participant's questions will be answered. Both the questions and subsequent answers will be recorded on an "ICF/HIPAA Questions Form," which will be maintained with the original Informed Consent Form. If the participant agrees to participate in the study, the Informed Consent Form will be signed (legal name) and dated by both the participant and a qualified member of the research team. Participants will receive a signed copy of the Informed Consent Form for their records.
4. Smoke a cigarette (own brand) outdoors to standardize the time to last smoke.
5. Complete baseline questionnaire:
  - Cigarette Brand Form - While viewing the participant's cigarette pack, the research staff will record the cigarette brand information on the form as appropriate. Additionally, a photocopy of the participant's cigarette packaging will be obtained for further verification of preferred brand and flavor.
  - Demographics and Sexual Orientation
  - Smoking History
  - Nicotine Dependence (FTND)
  - Pre-test measures of smoking related beliefs, attitudes towards quitting and knowledge of tobacco harms.

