### **5.10 Analytic Plan**

Descriptive statistics will be used to characterize the study population and smoking-related data. A factorial design will be used. The primary independent variable is warning label type (lesser-known harms vs well-known harms. Associations of independent and covariate variables with eye-tracking measures, recall, and knowledge will be assessed using unpaired t-tests or ANOVA (categorical predictors) and linear regression analysis (continuous predictors). Eye-tracking measures are continuous, and previously been observed to meet assumptions of normality. Recall is dichotomous and will be examined using logistic regression model to generate odds ratio, as in our previous work (Strasser et al., 2012; 2008). A primary outcome measure of this study is change in knowledge after exposure to graphic cigarette warning labels. This measure will be continuous when calculated on a scale and categorical when coded as increase in knowledge vs no change. Chi-square and regression analysis can be used to assess association of knowledge change with label type and by age group. Analysis will be conducted in a using Stata (Stata Corp., TX). Path analysis techniques for tobacco related mediation and moderation models will be used; covariates found to be significantly associated will be considered for inclusion in models as appropriate.

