### ***7.3 Data Processing***

The data entry screens will resemble the data collection forms as closely as possible to allow visual referencing during data entry. The data entry module will be configured for single data entry. The majority of participant data will be self-report and participants will either enter data into Qualtrics using computer, tablets or complete paper-and-pen forms during in-person visits. Some data might be collected by research staff, recorded on study-specific source documents/CRFs, and scanned in or entered directly into REDCap or MS Access. Data entry checks will be included in the entry screen designs, where appropriate, to limit the opportunity for erroneous entries due to mistyping. Such data entry checks would include value range comparisons, valid data type checks, required value checks, and/or skip pattern enforcement. Following initial telephone eligibility screening, research staff will perform subject registration.

Prior to lab session, research staff will randomize eligible participants. The randomization module will allow the research staff to randomize participants into one of the two trial arms. At the randomization attempt, the DMS will confirm milestones are accurate and that the randomization is valid. A randomization assignment will then be provided.

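### The eye-tracking comparison between arms estimates a difference between two label sets; on its own it cannot attribute that difference to the harm being lesser known

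*Combined protocol and SAP*

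**What the plan says.** - Section 4.1 sets the exposure: "Study participants will be randomized to view one set of graphic warning labels with either lesser-known or well-known harms of tobacco use". The same section says that eye movements are recorded for each label.
- Section 2.1 gives four labels per participant in random order (section 1 says about four). All 11 labels appear only later, for recognition and ranking. Section 2.2.1 counts 6 of the 11 as lesser known.
- Section 5.9.2 shows that each label has its own image and text statement. No section says that the two sets are matched on picture, wording or layout.
- Section 3, H2a under Aim 2, predicts: "H2a: Warning labels bearing images of lesser known tobacco use harms will have longer latency and fixation durations than warning labels bearing images of well-known" ones. Aim 2 describes the contrast as an effect of risk content.
- Section 5.10 states: "The primary independent variable is warning label type (lesser-known harms vs well-known harms". Gaze is compared by unpaired t-test, ANOVA or linear regression. No label effect is named.
- Section 5.8 lists, before viewing: "Pre-test measures of smoking related beliefs, attitudes towards quitting and knowledge of tobacco harms". Section 5.9.2 adds that participants pick harms from a list before and after viewing. Section 5.10 names knowledge only as an outcome (change), not as a predictor of gaze.

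**The concern.** Randomization balances the people in the two arms. It does not balance the stimuli. Every lesser-known label is seen in one arm only and every well-known label in the other, so anything about a picture or sentence that holds the eye is part of the arm difference. If one set happens to have more arresting images, fixation will differ between arms even if nobody's gaze depends on whether the harm was known. More participants would not help, because label differences do not shrink with sample size.

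The risk lies in the interpretation. A significant arm difference would naturally be reported as support for H2a, and section 6 says that the results may guide regulation of pack images. The lesser-known/well-known grouping is also taken as given and is never checked against what these smokers knew at pre-test.

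**Working it through.** **Inputs.** N = 70 (section 4.1: "This laboratory-based study will aim to enroll 70 current cigarette users to complete a 1-day, randomized, parallel design protocol"). Two arms (section 7.3: "The randomization module will allow the research staff to randomize participants into one of the two trial arms"); the ratio is not stated, so 35 per arm is assumed. Four labels per person. The documents give no alpha, power, effect size or SD, so 70 cannot be reproduced; section 5.2 rests it on earlier work "which was sufficiently powered to detect effects of a content attribute (congruency) on eye-tracking measures and image/text/message recall", which is a different attribute. Two-sided 0.05 and 80% power are assumed, so detectable difference = 2.8 × SE. Variance shares and knowledge rates are also assumptions.

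**1. Arm comparison.** Let r be the correlation between one person's gaze on different labels, and set the SD of a single observation to 1. For participant means, SE² = (2/35)(r + (1 − r)/4).
- r = 0.3: (2/35)(0.475) = 0.0271, SE 0.165, detectable 0.46 SD
- r = 0.5: (2/35)(0.625) = 0.0357, SE 0.189, detectable 0.53 SD
- r = 0.7: (2/35)(0.775) = 0.0443, SE 0.210, detectable 0.59 SD

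**2. What label differences add.** Suppose labels account for a share L of gaze variance and vary independently. The difference between two sets of four then gains variance 2L/4 = L/2, whatever the N. At L = 5% its SD is √0.025 = 0.16; at 10% it is √0.05 = 0.22. If the t-test is read as a test of familiarity and there is no such effect, it rejects with probability 2[1 − Φ(1.96/√(1 + (L/2)/SE²))], where the other components of SE² are scaled by 1 − L.

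| L (assumed) | rejection rate, r = 0.5 to 0.3 |
|---|---|
| 0 | 5% |
| 2% | 8 to 10% |
| 5% | 14 to 16% |
| 10% | 22 to 26% |
| 20% | 36 to 41% |

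Example, L = 5%, r = 0.3: SE² = (2/35)(0.285 + 0.665/4) = 0.0258; 1.96/√(1 + 0.025/0.0258) = 1.40, giving 16%.

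**3. Within-label contrast.** Regress each gaze measure on label effects, participant effects and an indicator that this person selected this label's harm at pre-test. Label differences cancel. SE² = (1 − r)/S, where S is the sum of squares of the indicator after label and participant means are removed. S was averaged over 3,000 simulated data sets of 35 people × 4 labels, that is, the lesser-known arm alone. Detectable differences in SD:

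| share knowing each harm | correlation of knowledge within person | r = 0.3 | r = 0.5 | r = 0.7 |
|---|---|---|---|---|
| 10% | 0 | 0.80 | 0.67 | 0.52 |
| 10% | 0.5 | 0.95 | 0.80 | 0.62 |
| 30% or 70% | 0 | 0.51 | 0.43 | 0.33 |
| 30% or 70% | 0.5 | 0.62 | 0.53 | 0.41 |
| arm comparison (step 1) | – | 0.46 | 0.53 | 0.59 |

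At 50% known and independent knowledge the values are 0.47, 0.39 and 0.30. Precision falls because people who know all or none of their four harms contribute nothing. At 10% known with independent knowledge that is 0.9⁴ + 0.1⁴ = 66% of them.

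**4. Why participant effects are needed.** In simulation (1,500 runs, no true effect, 30% and 95% knowing lesser- and well-known harms, r = 0.4), label effects alone gave a bias of about 0.3 SD when the trait behind knowledge correlated 0.5 with a person's general gaze. With participant effects added, the mean estimate was within 0.01 of zero.

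**The case against.** The strongest reply is that H2a is worded about labels and that 5.10 tests label type. The labels are FDA's own fixed set, four per arm is most of the 6 or 5 available, and this is a self-described exploratory pilot. For the question of whether one set holds gaze longer than the other, the randomized comparison is valid. That stands. A reader might infer that Aim 2 cannot be answered at all; the documents do not support this, because only the attribution to lesser-known content is open. The rates in step 2 likewise apply only when the test is read as evidence about familiarity and label differences are treated as chance variation.

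Other tempting readings also go too far:
- *The arms differ in the size of image and text areas, or reading time can be put in seconds.* The documents give no area sizes, word counts or viewing time per label. If viewing time is fixed, text and image durations would trade off.
- *The within-label contrast removes the confounding.* It removes picture and sentence differences only. Prior knowledge is not randomized, and a link between one person and one harm, such as an affected relative, survives both sets of effects.
- *It costs little precision.* That depends on the setting. It gains in most settings at r = 0.7, but loses clearly at r = 0.3 if few know the harms or if knowledge clusters within people.
- *Agreement in sign between the two estimates is enough.* With no familiarity effect, signs agree half the time. At L = 10% this would cut false attributions only from about 24% to 12%.

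Finally, 5.10 mentions covariates and moderation models, so baseline knowledge is not excluded. It is not named either, and no label term appears.

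**Conclusion.** The point holds as a limit on interpretation. Harm type is fully aliased with the specific images and sentences, and the plan has nothing to separate them. The arm comparison is sound for these two label sets as shown and should stay; what it cannot do alone is establish the reason for a difference. This follows from the design and rests on none of the assumed numbers.

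The size of the risk is not known from the documents. If labels account for 5 to 10% of gaze variance (assumed), reading the t-test as a familiarity test would mislead about 14 to 26% of the time instead of 5%. The supportive analysis has a detectable difference of roughly 0.3 to 0.95 SD over 10 to 70% knowing each harm, knowledge correlation 0 to 0.5 and gaze correlation 0.3 to 0.7. It may be weaker than the arm comparison. The point does not challenge the sample size.

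**What to change.** 1. In sections 3 and 5.10, state that the arm comparison of eye-tracking measures estimates a difference between the two label sets as shown.
2. Confirm that the pre-test checklist includes each displayed harm. H2c implies it, but no section says so. Then tabulate pre-test knowledge of each displayed harm, by label, to check the grouping.
3. Add to 5.10 a supportive participant-by-label model of each eye-tracking measure, with label effects, participant effects and an indicator that the participant selected that label's harm at pre-test. Report the coefficient with its confidence interval, as associational.
4. Attribute the arm difference to familiarity only if that interval, not merely its sign, supports it. Otherwise report a difference between label sets.

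The cost is plan wording and one extra model. No new data are needed if the checklist covers the displayed harms; if it does not, the missing items must be added. The drawbacks are that prior knowledge is not randomized, that the information comes mainly from the lesser-known arm, and that the estimate may be imprecise. If it is, the label-set wording is still the correct report.
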